There have been attempts to use non-invasive brain stimulation to improve dual-task walking in humans, including neurological involved population. To date, there is no study that examines the efficacy of non-invasive brain stimulation in dual-task walking in individuals post-stroke. In addition, previous research has primarily focused on stimulating left dorsal lateral prefrontal cortex (DLPFC). Most studies found that up-regulating excitability of the left DLPFC improved dual-task cost but had little effect on gait performance. One possible explanation is that the DLPFC does not play an important role in governing gait performance during dual-tasking even though it has significant impact on task switching. Therefore, other neural networks, such as the supplementary motor area (SMA) that has been found to be associated with gait recovery may also play an important role in modulating dual-task gait. The purpose of this pilot project is to examine the efficacy of rTMS applied to different neural loci in improving dual-task gait in individuals post-stroke.

**Research question:** Would rTMS applied to different neural loci result in different dual-task gait performance in patients with stroke?

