# 4. Research Procedures:

- a. In the space below, describe in detail the research procedures (do not use an attachment):
  - Screening and Baseline assessment: Upon the consent, participants will be screened for their eligibility in addition to the criteria. We will use Mini Mental State Exam (MMSE; 3.Appendix 1) and TMS safety-screening questionnaire (3.Appendix 2) to ensure that participants do not have any cognitive impairments or contraindications for TMS. In addition, they will be asked to perform a 10 meter walk test to ensure they are able to walk 10m independently.

Once the eligibility is determined, each participant will be assessed with the Fugl-Meyer Motor Assessement (FMA; 3.Appendix 3) scale to quantify their motor impairment and a Trail-Making Test (TMT; 3.Appendix 4) to assess their executive function.

2. **Assessements**: Each participant will be tested with a gait assessment, followed by a counting task performance and a neurophysiological assessement.

2a. Gait Assessment: The gait assessment consists of walking at self-selected speed on the GaitRite carpet walkway. Gait performance (time taken, gait speed, stride cycle, step length) will be recorded by the GaitRite. The assessment will be repeated 3 times with about a 1 minute break between trials.

The walking test will then be repeated for another 3 trials under a dual-task condition in which the participants will perform the walking task in conjunction with a counting task. Before the 'Go' command, the tester will verbally provide a random number ranged from 30 to 100. They are then asked to perform the TUG test and count backward by 3 from the given number (e.g. 87, 84, 81, ...). During the dual-task TUG test, the participants will be asked to priortize the counting task.

In addition to the GaitRite measurement, the gait assessment will be videorecorded such that participants' performance on the counting task can be quantified offline (number of correct responses).

2b.Counting Task assessment: After the participants finish the gait assessment, the counting task will be repeated 3 times while they are seated.

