During each visit, they will receive 5Hz rTMS delivered to the target area (hot spot of the right tibialis anterior at the M1, left SMA, or left DLPFC). The 5Hz rTMS will be delivered in the form of 24 10-second trains with a 30second intertrain interval (a total of 1200 pulses) via a airfilled figure of 8 coil (Figure 2). The stimulation intensity will be set at 90% of individual RMT. We have previously shown that this protocol was effective to upregulate corticospinal excitability.

Figure 2. Air-filled coil for rTMS

After the rTMS protocol, corticospinal excitability will be reassessed using single pulse TMS again (procedure 2c). Participants will then perform the gait assessment (procedure 2a) and the counting task (procedure 2b).

Each participant will be tested for 3 visits (each visit will be 7±2days apart between two successive visits). Each visit will start with the assessment and be followed by a rTMS protocol. The target area for the rTMS protocols varies across visits (e.g. visit 1: Left SMA, visit 2: Left M1, and visit 3: Left DLPFC). The order will be pseudo-randomized and counterbalanced within each group.

4. Outcomes and data analysis: The primary outcome of this project is participant performance on the TUG test under single and dual-task conditions. The time taken to complete the TUG test under the two conditions will be used to derive dual-task cost (TUGdual – TUGsingle/TUGsingle). The dual-task cost will be compared across three rTMS protocols using repeated measure ANOVA. The secondary outcomes of the projects include gait parameters obtained from the

The secondary outcomes of the projects include gait parameters obtained from the GaitRite, MEPs measured under procedure 2c. These measures will be analyzed using repeated measure ANOVA as well.

b.	Is video recording a part of the s	tudy?	🛛 Yes 🗌 No	
	With sound $\square$	Without sound		
C.	Is audio recording a part of the s	tudv?		Yes 🗆 No

*If you answered "yes" to question #4b or 4c, describe the purpose of the recording and who will have access to these recordings.* 

The video recording will be used to quantify the number of corrected responses participants made on the counting task.

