# POTENTIAL RISKS AND PROTECTION OF PARTICIPANTS

7. Explain the potential risks to the human participants involved in this research. All risks must be identified and listed on the consent form (if applicable).

RISK	STEPS TO MINIMIZE RISK
Loss of confidentiality	The investigators will attempt to maintain confidentiality to the extent that is allowed by law. The study will take place at Texas Woman's University, School of Physical Therapy – Dallas Campus. Codes, rather than names, will be used in the data analysis and in the final report. The data will be stored in a locked file cabinet. The data recorded on papers will be stored for approximately 5 years and then will be shredded. The data recorded on disks will be stored for 5 years and then will be deleted. It is anticipated that data will be published in books and/or journals. However, names or other identifying information will not be included in any publication.
4.Loss of time The study requires 3 sessions and each session lasts 2 to 2.5 hours. The loss of time could potentially impact participants' life.	To minimize the impact of loss of time, all visits will be scheduled based on participant's convenience. For example, on the same day that they come to Dallas Stroke Center for speech therapy appointments or during weekends.
Loss of balance	To minimize this potential risk, the tester will
The gait assessment involves walking and	walk alongside the participants during testing.
turning in which participants may experience loss of balance.	All testers are trained to detect and assist loss of balance during gait.
5.Fatigue	To minimize this potential risk, we will schedule
The study requires 3 sessions and each session lasts 2 to 2.5 hours. The length of the testing is necessary to obtain data needed. However, this might potentially result in fatigue due to the lengthy testing.	sufficient resting time between tests. In addition, participants may withdraw anytime if they are too fatigued to continue.
RISK	STEPS TO MINIMIZE RISK

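### The primary ANOVA on dual-task cost names no time point, so the pre-rTMS value collected at every visit has no role; it should be the covariate in a post-rTMS analysis.

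*Combined protocol and SAP*

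**What the plan says.** All references are to the combined protocol and SAP.

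- **Pre-rTMS assessment.** Section 4 (Research Procedures), item 3: "Each visit will start with the assessment and be followed by a rTMS protocol". Under item 2, that assessment includes gait under single- and dual-task conditions.
- **Post-rTMS assessment.** After stimulation, item 3 repeats the excitability measurement and continues: "Participants will then perform the gait assessment (procedure 2a) and the counting task (procedure 2b").
- **Primary analysis.** Item 4 derives dual-task cost from TUG times under the two task conditions, then states: "The dual-task cost will be compared across three rTMS protocols using repeated measure ANOVA".
- **Secondary analysis.** For GaitRite parameters and MEPs: "These measures will be analyzed using repeated measure ANOVA as well".
- **Research question.** Section 1: "Would rTMS applied to different neural loci result in different dual-task gait performance in patients with stroke".

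No section says whether the compared dual-task cost is the pre-rTMS value, the post-rTMS value, their difference or both.

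**The concern.** Three visits with two assessments each give six dual-task costs per participant: three before and three after stimulation. The analysis sentence names one factor, the stimulation protocol, and so does not say how six values enter a comparison of three protocols. Three ordinary analyses fit the wording:

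1. a one-factor ANOVA on post-rTMS values, with the baseline unused;
2. a site-by-time ANOVA tested by the interaction, which is the same test as an ANOVA on change scores;
3. a site-by-time ANOVA tested by the site main effect, which averages unaffected pre-rTMS values into the comparison.

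They differ in power, and with 10 participants the choice can decide the result. If it is made after the data are seen, the nominal error rate no longer holds. None of the three is the most useful analysis over most of the range of r examined: a same-visit baseline is already collected, and the plan does not adjust for it.

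**Working it through.** **Check of the text.** There is no stated figure to reproduce. Section 2 gives 10 participants without a power calculation, and no alpha, effect, SD or correlation appears anywhere. That the baseline has no stated role follows from reading items 2 to 4 of Section 4 together.

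**Inputs to the illustration.** From the documents: n = 10, three sites, one pre and one post value per visit. Assumed: alpha 5%, complete data, no visit trend, equal variances and correlations. One site differs from the other two by d after stimulation, in units of the within-participant SD (visit-to-visit variation about a participant's own mean). r is the within-participant correlation of pre and post values at the same visit.

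**Formulas.** With site means 0, 0, d, the sum of squared deviations is 2d²/3. The F-test for site has 2 and 18 degrees of freedom, with noncentrality:

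- post-only: λ = 10 × 2d²/3;
- change or interaction: the error variance is 2(1 − r), so λ/[2(1 − r)];
- pooled main effect: the effect is d/2 and the variance (1 + r)/2, so λ × (1/4)/[(1 + r)/2] = λ/[2(1 + r)].

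At d = 1.2, λ = 10 × 2 × 1.44/3 = 9.60. At r = 0/0.3/0.5/0.7 the change-score noncentrality is 4.80/6.86/9.60/16.00 and the pooled one 4.80/3.69/3.20/2.82. Power for these three comes from the noncentral F distribution. Power for the adjusted analysis (17 error df) comes from simulation with 40,000 replicates per cell (simulation SE at most 0.25 points).

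| Analysis, d = 1.2 | r = 0 | 0.3 | 0.5 | 0.7 |
|---|---|---|---|---|
| Post-only | 72% | 72% | 72% | 72% |
| Change or interaction | 42% | 57% | 72% | 92% |
| Pooled main effect | 42% | 33% | 29% | 26% |
| Post, adjusted for same-visit pre | 69% | 74% | 82% | 94% |

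**Break-even.** At d = 1.2, adjusted against post-only is 70.4 against 72.3% at r = 0.15, and 73.7 against 72.6% at r = 0.3. Adjustment therefore starts to gain between those values.

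**High r.** At r = 0.9 and d = 0.8, the change score has 97.4% power and the adjusted analysis 97.1%, practically a tie.

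**Error rate.** Each analysis fixed in advance rejects in about 5% of null simulations. Taking the smaller p of post-only and interaction after seeing the data gives about 8.5 to 10%. With the pooled main effect also available, it is about 10 to 12%.

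**The case against.** The order of events and the research question make a post-rTMS comparison the natural reading, and a post-only analysis fixed in advance is valid. This is a 10-participant pilot described in an ethics application, so a terse analysis section is to be expected. Much of that stands. The text still does not state the post-only reading, and under it a baseline measured at every visit goes unused. The pilot aims at efficacy as well as feasibility, and it names a primary outcome and a test.

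A reader might infer that the plan has a demonstrated power loss or an inflated error rate. The documents do not support that. Every d and r above is assumed, no figure in the plan is wrong, and the 10 to 12% arises only if the most favourable of three analyses is picked afterwards. Nothing says that this is intended.

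A reader might also infer that baseline adjustment is always best. It is not: it loses slightly to post-only when r is near zero and gains nothing material over a change score when r is very high. A low r is possible, because dual-task cost is a ratio. The case for adjustment is that it is close to the best of these analyses across the range examined, whereas each alternative does badly somewhere in it.

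The illustration assumes no visit trend, so it cannot settle whether a visit term is needed.

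**Conclusion.** The concern holds as an unspecified primary analysis with a cheap improvement at hand. It is worth correcting before the data are seen, but it does not make the plan invalid. Under the stated assumptions at d = 1.2, adjusting for the same-visit baseline changes power against post-only by about −3, +1, +10 and +22 points at r = 0, 0.3, 0.5 and 0.7 (69.3, 73.7, 81.8 and 94.3% against about 72%). The pooled main effect is the reading most in need of exclusion, at 42% falling to 26%. The missing role for the baseline rests on the text alone; the sizes rest on assumed d, r, alpha and complete data.

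A separate point adds no weight here but must be settled first. Section 4, item 2a describes the single-task test thus: "The gait assessment consists of walking at self-selected speed on the GaitRite carpet walkway". It names TUG only for the dual-task trials: "They are then asked to perform the TUG test and count backward by 3 from the given number". Item 4 computes the cost from TUG under both conditions. Item 2a also presents the dual-task trials as a repeat of the walking test, and the risk table in Section 7 refers to turning during gait assessment, so a single-task TUG may have been intended. The text does not say so.

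**What to change.** In Section 4, item 4, state that the primary analysis is of post-rTMS dual-task cost, with participant and site effects and the same-visit pre-rTMS dual-task cost as covariate, tested by the site effect. Use the same baseline adjustment for MEPs and for GaitRite parameters, taking single- and dual-task gait values separately.

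The cost is analysis wording only, with no new visits or measurements. One error degree of freedom is lost (18 to 17), with 2 to 3 points of power against post-only if r is near zero. If a visit term is added, error df falls to 15 and power at d = 1.2 becomes 67/72/80/93% at r = 0/0.3/0.5/0.7.

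Separately, reconcile items 2a and 4 on which test supplies the single-task time, since neither the pre- nor the post-rTMS dual-task cost is defined until that is done.

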# 5. What is the time commitment for the participants? Include the number of sessions, maximum time commitment per session, and the maximum cumulative time commitment.

Each participant will be tested over 3 sessions (7  $\pm$  2 days between two successive sessions). Thus, the whole experiment will take place over ~ 3 weeks. Each session is estimated to take about 2.5 hour. Thus, the maximum cumulative time commitment for each participant is approximately 7.5 hours.

# 6. Site / location of the study.

a. Will participants be affiliated with a specific non-TWU agency, institution, or organization?......

If yes:

Name of the site(s)?

Affiliation of the principal investigator to this site(s)?

Affiliation of the **participants** to this site(s)?

Agency approval letters are required by the IRB before data can be collected at a site. If you answered "yes" to 6a, attach the signed agency approval letter on letterhead from each agency. If agency approval cannot be obtained prior to submitting the IRB application, explain here.

b. Describe the setting of the study (i.e. physical location, surroundings, privacy aspects, etc.)

The study will take place at the TWU – Dallas Campus. Participants will undergo TMS procedure on the  $1^{st}$  floor in the Human Neurophysiology Lab. The gait assessment will take place on the  $1^{st}$  floor in the Motor Skill Lab.

# POTENTIAL RISKS AND PROTECTION OF PARTICIPANTS

7. Explain the potential risks to the human participants involved in this research. All risks must be identified and listed on the consent form (if applicable).

RISK	STEPS TO MINIMIZE RISK
Loss of confidentiality	The investigators will attempt to maintain confidentiality to the extent that is allowed by law. The study will take place at Texas Woman's University, School of Physical Therapy – Dallas Campus. Codes, rather than names, will be used in the data analysis and in the final report. The data will be stored in a locked file cabinet. The data recorded on papers will be stored for approximately 5 years and then will be shredded. The data recorded on disks will be stored for 5 years and then will be deleted. It is anticipated that data will be published in books and/or journals. However, names or other identifying information will not be included in any publication.
4.Loss of time The study requires 3 sessions and each session lasts 2 to 2.5 hours. The loss of time could potentially impact participants' life.	To minimize the impact of loss of time, all visits will be scheduled based on participant's convenience. For example, on the same day that they come to Dallas Stroke Center for speech therapy appointments or during weekends.
Loss of balance	To minimize this potential risk, the tester will
The gait assessment involves walking and	walk alongside the participants during testing.
turning in which participants may experience loss of balance.	All testers are trained to detect and assist loss of balance during gait.
5.Fatigue	To minimize this potential risk, we will schedule
The study requires 3 sessions and each session lasts 2 to 2.5 hours. The length of the testing is necessary to obtain data needed. However, this might potentially result in fatigue due to the lengthy testing.	sufficient resting time between tests. In addition, participants may withdraw anytime if they are too fatigued to continue.
RISK	STEPS TO MINIMIZE RISK

Headaches It has been shown that with repetitive stimulation on the scalp (in rTMS protocols), a small number of participants (< 28% cases) would develop transient headaches. The developed headaches usually resolved within 3-4 hours and respond well to over-the- counter pain medicine, such as 6.Tylenol.	To minimize this potential risk, we will exclude participants who are prone to develop headaches (e.g. history of migraine). We will use subthreshold intensity for rTMS protocols that will reduce the likelihood of developing headaches. In addition, the tester will stop the testing when they develop headaches during the test. 6.If participants do develop headaches and require pain medication, we will ask them to take the pain medication that has been approved by their primary care physicians.
RISK	STEPS TO MINIMIZE RISK
Changes in auditory threshold There is a risk of alteration in auditory threshold after TMS protocols as TMS produces loud click when it is charged. The changes in auditory threshold are transient (lasts about 1 day) and not different from going to a music concert.	To minimize the risk, we will provide earplugs during TMS testing.
RISK	STEPS TO MINIMIZE RISK
Seizure Risk of seizure is associated with high frequency rTMS and is higher in those who have history of seizure, on medication that are known to reduce seizure threshold. Risk of seizure is also higher when the rTMS parameters are set outside of the safety limits.	We will use a safety-screening questionnaire adapted from the recommendation of the international committee  . This questionnaire will help us to identify those at high risk of developing seizure and they will be excluded from participation. The rTMS protocols adopted in this project are within recommended safety limits  and we have previously conducted rTMS experiments using the same protocols without any adverse events  .

(Use continuation pages if necessary)

8. Will participants be told about the intent of the study prior to participating? ... X Yes No If "no," provide an explanation of why deception is necessary and the debriefing method to be used to fully inform the participants of the study's intent.

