# 2. Participant Information:

a. Description of participants in study:

Ten men and women with a diagnosis of left hemisphere stroke and age >18 years will be recruited to participate in this pilot project.

- b. Approximate number of participants: 10
- c. Vulnerable populations as participants (check all that apply):

Prisoners[	
Pregnant women	
Fetuses / neonates	
Minors	

NOTE: Researchers must comply with the federal mandate to report child abuse. See instructions for details.

d. Age (or age range) of participants: > 18 years

Provide the rationale for inclusion/exclusion on the basis of age:

- 1. This study will not include individuals age below 18 years for a few reasons. Stroke is relatively uncommon in persons younger than 18 years. Further, rTMS safety data in children and adolescents are less well-established. We exclude individuals younger than 18 years for both scientific merit and safety concern.
- e. Sex of participants ...... Both

Provide the rationale for inclusion/exclusion on the basis of sex:

If yes, provide a description of the exclusion criteria and the rationale for using these criteria:

g. List and provide rationale for any other inclusion/exclusion criteria:

Inclusion criteria:

- Age above 18 years
  Stroke is very unlikely in individuals age below 18 years. Further, there are limited data to support the safety of rTMS in individuals younger than 18 years.
  - Diagnosis of Left hemispheric stroke at least 6 months ago
    Left dorsolateral prefrontal cortex has been shown to play an important role in human dual-task performance. We therefore specifically target those with left hemispheric lesion since they demonstrate greater deficits in dual-tasking. We exclude acute and subacute (< 6 months) stroke because spontaneous recovery is very likely to occur

during acute and subacute phases. This will lead to difficulty in result interpretation with the current single group design.

- First time stroke OR complete gait recovery from prior stroke
  Individuals with more than one stroke often have more than one lesion location or involve more than one hemisphere. This would potentially complicate the rTMS application. We therefore exclude those with multiple strokes such that our sample can be more homogenous.
- 4. Able to walk independently for at least 10 meters with or without walking aids 2.Participants are required to walk independently for the behavioral testing.

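### The primary repeated measures ANOVA has no rule for a session stopped before the post-rTMS walk; in its classical form it would drop that participant's completed visits as well

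*Combined protocol and SAP*

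**What the plan says.** Section 2 plans for 10 participants ("Approximate number of participants: 10"). Section 4 gives each of them three visits ("Each participant will be tested for 3 visits"), with a different stimulation target at each. Within a visit the order is baseline gait, counting and single-pulse TMS, then rTMS, then repeat single-pulse TMS. After that, "Participants will then perform the gait assessment (procedure 2a) and the counting task (procedure 2b"). The post-rTMS walk therefore comes late in the session, with only the seated counting task after it.

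Item 4 of section 4 (Outcomes and data analysis) states the primary analysis: "The dual-task cost will be compared across three rTMS protocols using repeated measure ANOVA".

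The risk table in section 7 foresees two ways in which a session can end early. For headache, "the tester will stop the testing when they develop headaches during the test", and the same row says that with repetitive stimulation "a small number of participants (< 28% cases) would develop transient headaches". For fatigue, "participants may withdraw anytime if they are too fatigued to continue", and that row names the cause: "The study requires 3 sessions and each session lasts 2 to 2.5 hours".

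The documents contain no missing-data rule, analysis population, rule on repeating or replacing a stopped session, or dropout allowance. The nearest text is the section 2 exclusion for anticipated inability to complete all three visits. It acts at entry only.

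**The concern.** Each site's dual-task cost after stimulation comes from the single- and dual-task walks done after rTMS. Item 4 does not say whether the post-rTMS value or the change from baseline is compared, but both need that walk. A stop between the start of rTMS and the walk therefore removes that visit's primary value.

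A classical repeated measures ANOVA works on complete triplets. With one value missing and no other rule, the default is to drop the person, including valid visits at the other two sites. In a sample of 10 that wastes data. It also restricts the comparison to people who tolerated all three sites. If tolerability differs by site, or goes with poor gait, the analysed set is partly selected by the treatment. Losing whole participants also disturbs the counterbalanced order.

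**Working it through.** **No figure to reproduce.** The plan gives no stop rate, alpha, power, SD or sample-size derivation. The stop rates, correlations and clustering below are assumptions.

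**Inputs from the documents.** n = 10 (section 2); 3 visits each, so 30 sessions (section 4); headache below 28% (section 7).

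**Step 1: which stops matter.** A stop costs the primary value if it comes after rTMS starts and before the post-rTMS walk is finished. A stop after the walk costs nothing on the primary outcome. A stop before rTMS means that the session was not delivered. Let q be the assumed probability per session of losing the primary value.

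**Step 2: complete participants.** If stops are independent, expected complete participants = 10(1−q)³, the chance of losing at least one participant = 1−(1−q)³⁰, completed sessions = 30(1−q), and sessions kept by a complete-case analysis = 30(1−q)³.

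| q | Complete of 10 | P(at least one lost) | Sessions completed | Sessions kept |
|---|---|---|---|---|
| 5% | 8.6 | 79% | 28.5 | 25.7 |
| 10% | 7.3 | 96% | 27.0 | 21.9 |
| 20% | 5.1 | >99% | 24.0 | 15.4 |

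For q = 10%: 10 × 0.9³ = 7.29, 30 × 0.9 = 27, and 30 × 0.9³ = 21.87. About 5.1 completed sessions are discarded on average.

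**Step 3: the 28% figure.** The sentence speaks of participants, so the per-participant reading is the natural one: 10 × (1−0.28) = 7.2 complete, if every headache led to a lost value. Read per session it would give 10 × 0.72³ = 3.7, but the wording does not favour that. On either reading 28% bounds headache, not stopped sessions.

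**Step 4: what the method does with one gap.** In simulated data for 10 people and 3 sites with one value removed, a standard repeated measures ANOVA routine refused to run because the data were unbalanced. After complete-case deletion it used 9 people, 27 values and 2 × (9−1) = 16 error df, against 2 × (10−1) = 18 with full data. A random-intercept mixed model kept 10 people and 29 values.

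**Step 5: precision.** The variance of a pairwise site contrast was simulated with n = 10, compound symmetry, within-person correlation 0.5 or 0.7 and independent stops. Generalised least squares on all completed visits was compared with complete cases. The range covers both correlations and two ways of averaging (ratio of mean variances, mean of per-draw ratios).

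| q | SE ratio, all visits / complete cases | SE reduction |
|---|---|---|
| 5% | 0.95-0.96 | about 4-5% |
| 10% | 0.90-0.92 | about 8-10% |

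The covariance is treated as known, so the cost of estimating it in a small sample is not included.

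**Step 6: clustering.** Let q vary between people as a beta distribution with mean 10%. At intraclass correlation 0.3 or 0.5, expected complete participants rise from 7.3 to 7.9 or 8.3. At 0.5, the sessions recovered by using all visits fall from about 5.1 to 27 − 3 × 8.265 = 2.2. The gain in step 5 shrinks accordingly.

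**The case against.** The strongest reply is that the gap may seldom open. Section 7 excludes people prone to headache, uses subthreshold intensity, schedules rest and reports earlier use of the same protocols without adverse events. Section 2 excludes people not expected to finish, and section 11 gives the gift card on completing three visits. Many stops could also fall outside the window that matters. This stands: the stop rate may be well below the headache ceiling, and 28% should not be used as a stop rate.

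Second, item 4 does not say that incomplete participants are deleted, and nothing rules out repeating a stopped session. That also stands. A reader might infer that the plan itself removes anyone with one stopped session. The documents do not support that; deletion is the default of the named method when no rule is given.

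Third, a reader might infer that the primary result is biased by tolerability. The documents give no headache or fatigue rates by site, so this is a possibility and not a finding. A mixed model would not fully cure it either.

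Fourth, withdrawal for fatigue may mean leaving the study, so there may be no later visits to keep. That is true, but visits already completed would still be available.

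What the reply does not remove is the gap itself. The protocol foresees early stops and names a method that needs complete triplets, with no rule for the case where they collide. Even at an assumed independent 5% per session, the chance of losing at least one participant is 79%.

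**Conclusion.** The point holds in conditional form. A stop between the start of rTMS and the post-rTMS walk would lose that visit's dual-task cost, and the stated ANOVA, run in its classical form, would then discard the person's other visits.

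The size depends on a rate that the documents do not give: 8.6 or 7.3 complete participants of 10 at an assumed independent 5% or 10% per session, and 7.2 if 28% is a per-participant ceiling on lost values. The precision recovered is modest, about 4-5% or 8-10% of the standard error, and smaller if the same people stop repeatedly. In a pilot of 10 it is still worth having, because the change is cheap. The safety stop itself is not in question.

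**What to change.** In item 4 of section 4, replace the repeated measures ANOVA of dual-task cost with a linear mixed model: participant random, site and visit period fixed, every completed visit included under its assigned site, with a small-sample df correction such as Kenward-Roger. State that completed visits stay in the analysis when another visit of the same person is incomplete. For each stopped session, report the site, the reason and whether the post-rTMS walk was done, and tabulate stops by site. Leave the safety stop and the rules for attending later visits unchanged.

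The cost is a few sentences of protocol text and one extra line on the case report form. With complete data the site-only model gives essentially the same test as the ANOVA. The period term uses 2 error df (18 − 2 = 16 with full data) and in return adjusts for order when lost visits upset the counterbalancing.

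The limit is that the model assumes stops are missing at random given the observed data. It does not remove bias from site-related stops driven by unobserved factors, which is why stops by site need to be reported beside the result.
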